F4. Review to detect presence or absence of hypoxemia indicative of ARDS: In order to further eliminate the unnecessary detailed record review, a focused review of the transfusion episode will be performed to detect hypoxemia occurring within six hours of completion of transfusion. Medical records will be reviewed for the respiratory status within six hours after the completion of the study unit transfusion to detect the following: Oxygen saturation (SpO2) less than 90% by pulse oxymetry without or with oxygen therapy; ratio of SpO2/FiO2 <315; and ratio of PaO2/FiO2 <300 on arterial blood gas analysis. FiO2 will be calculated for patients receiving oxygen by cannula or mask as follows: 1 liter = 0.21; 2 liters = 0.23; 3 liters = 0.25; 4 liters = 0.35; 6 and 7 liters = 0.45, and 8, 9, and 10 liters = 0.49 (Rice TW 2007).

If hypoxemia is documented, a detailed medical record review will be performed by the record review coordinator. The full extended data form will be completed. A Power Point summary of the major events and timeline will be prepared. The completed extended data forms and summaries will be sent to the Triage MD for further review.

Precise incidence rates for hypoxemia as defined in this manner in hospitalized patients are not available. Most of the data on incidence of acute respiratory failure (ARF) are reported in patients who are treated in the intensive care unit (ICU). For example, Flaatten et al have reported an incidence of ARF of 63% among 832 patients treated in the ICU. In 13,346 ICU admissions, 1,231 (9.2%) patients were found to have acute respiratory failure by Luhr et al. Pettila et al have described an incidence of ARF of 32.5% in 520 ICU patients while Vincent et al found that 32% of the 458 ICU patients had ARF at admission to the ICU and 35% of the 991 ICU patients developed ARF during their stay in ICU. Roupie et al report that 43% of the ICU patients required mechanical ventilation. A combined rate of 16% for ARDS and ALI in 1977 ICU admissions has been observed by Bersten et al. These data show a wide range for ARF in ICU patients. In order to be more conservative in our estimates for the number of charts requiring detailed review, we have estimated that 60% of the study patients would have hypoxemia/acute respiratory failure and would therefore require detailed chart review along with a review by a triage critical care physician (see below).

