F16. Identification of study recipients, record retrieval, medical records review, and data collection: Hospital blood bank staff will identify the disposition of study blood components. For those components that were issued for transfusion, the blood bank staff will complete a form that indicates that the component was issued for transfusion, name of the patient, the patient's medical record number, blood unit identification number, the date and time the product was issued, type of component and whether there was any adverse event reported within 24 hours after the issue of the product.

The record review coordinator will record information from those patients who had a chest x-ray within 24 hours after the blood component was issued for transfusion. Each center will need to work with their hospitals to find the best way to review radiology records. The radiologist's interpretation of each chest x-ray will be transcribed verbatim on to a data collection form

provided by the Coordinating Center and forwarded to the site investigator. The site investigator will review the radiology reports and determine which patients' charts will require further detailed review. The site investigator review and decision will be documented on to a data collection form. The record review coordinator will request the medical charts from the medical records department. At some hospitals, electronic records may be available and the coordinator may access the electronic records after having been approved to do so. Digital images of chest x-rays will be obtained for cases that need the triage physician and Expert panel reviews when available.

F17. Record review coordinator qualification and training: Qualifications of personnel engaged in record review can include medical technologists; nurses with critical care unit or operating room experience; respiratory care professionals; and other suitable individuals. The designated individuals at each Center will be provided with reading material and will undergo training at [name] program which will involve review of actual cases of TRALI, Acute lung injury (ALI), TACO, and transfusion recipients without these complications. The nurses working with [name] prospective study on TRALI who are very familiar with record reviews will provide training. The training will also include writing up case summaries for the Medical Review Board.

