HLA antibody prevalence in blood donors*	Percent of TRALI that are antibody mediated**	Average # components per transfusion episode***	'control' r	Number required in each of 'case' and 'control' recipients arms for different power estimates		
			80%	85%	90%	
8.5%	80%	6	806	917	1067	
9.0%	80%	6	886	1007	1175	
10.0%	80%	6	1034	1178	1379	

* Results for LAPS show the HLA prevalence to be about 16% for women and about 1% for men, hence overall prevalence of HLA antibodies in units transfused in hospitals participating in LAPS-II is likely to be in the range of 8.5% to 10%.

** Approximately 80% to 85% of TRALI cases are thought to be antibody mediated. The required sample size decreases as the immune mediated percentage increases, thus conservatively 80% is used in the table.

*** Recipients receiving an apheresis component are assumed to receive no other components during the transfusion episode. Recipients receiving an FFP (or other plasmas) component are assumed to receive on average a total of 6 components during the transfusion episode, and as a worst case scenario the additional components are assumed to be high risk TRALI components.

H4. Sample size and power selected for the study: From the above table and the details provided in Appendix D, the sample size selected was 1,175 for the antibody positive components and 1,175 for the antibody negative components. This number will give 90% power to detect a TRALI rate difference between the two groups of recipients. This conservatively assumes that a transfusion episode consists of 6 components although apheresis platelet component transfusion is most often a single unit transfusion episode. The percentage of TRALI that is antibody mediated is assumed to be 80% which may also be a conservative estimate. To the above number, a 10% margin is added to account for missing records etc. Therefore, the total number of antibody positive and antibody negative components is 1,295 for each group.

Based on OSMB recommendations we plan to conduct an interim analysis to see if the estimated sample size is adequate. The interim analysis will assess the average number of components per transfusion episode (assumed to be 6) and the TRALI incidence per component of unknown HLA status (assumed to be 0.18%). If the average is much greater than 6 or the incidence much lower than 0.18%, then increasing the sample size will be considered. A detailed description of the interim analysis is provided in Appendix H.

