- the proportion of TRALI due to HLA antibodies (i.e. immune-mediated)

Additional analyses will involve estimating TRALI incidences and other incidences. Analysis will be conducted to assess the incidence of TRALI and possible TRALI per unit transfused and per transfusion recipient. For this analysis the number of units transfused per episode per patient will be derived from the data available in the data collection forms. Incidence will also be calculated, when possible, for (a) TRALI without other risk factors and TRALI with other risk factors, (b) among those with other risk factors, incidence will be calculated for ALI which cannot be distinguished from TRALI and for ALI that is not TRALI but that occurred within 6 hours or >6 hours of transfusion.

Analysis of other incidences is described below. In addition to the transfusion complications described above, incidence for transfusion-associated cardiac overload will be based on cases that are classified by the Medical panel as TACO.

Using appropriate statistical methods, associations will be explored between different transfusion complications described above (TRALI, no-TRALI, possible TRALI, ALI of undetermined origin, TACO) and the underlying clinical information, such as, demographics, diagnosis (CPT codes), co-morbid conditions (e.g. renal failure), degree and severity of hypoxemia, chest x-ray and cardiac abnormalities. Data, when available, will be correlated with the presence of HLA and HNA antibodies (signal strength and/or specificity of antibodies) in the recipients as well as the involved donors and their HLA and HNA phenotypes to assess the antibody specificity and the corresponding cognate antigens in donor/recipient pairs among different groups of patients with complications described above. Frequencies of clinical symptoms of transfusion complications will be ascertained. Recipient outcome data, when available, will be tabulated for different types of transfusion complications. Clinical characteristics of the cases that were reported to the blood bank before the study and after the study will be compared.

M. Timeline

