For each HLA positive donor in the study, we consider all of this donor's components in the study period, and enroll recipients of these components as case subjects. In our case recipient group, we will know that one component is HLA positive and that any other components (the number of other components can vary for each recipient) the recipient receives have unknown HLA status. For each HLA negative donor in the study, we consider all of this donor's components in the study period, and enroll recipients of these components as control subjects. In our control group, we will know that one component is HLA negative and that any other components the recipient receives have unknown HLA status. Assume the number of components a recipient receives can be anything from 1 to 11, and averages 6. (Of minor note, the case and control groups will have a higher mean number of components than the overall recipient mean. The reason is that recipients with greater number of components have a higher chance of selection into the study, i.e. since we select components and find the recipient that

received that component, then a recipient with 11 components has 11 chances to be selected, while the recipient with a single component has just 1 chance to be selected).

Using the estimates of TRALI incidence per component (conditional on whether a component is HLA positive, HLA negative, or unknown HLA status), we can estimate the TRALI incidence per case recipient and per control recipient by first calculating the probability of not developing TRALI when receiving on average of 6 components (range 1-11), and then taking the complement of that probability to estimate the probability of the recipient developing TRALI after receiving these components. As an example, a case recipient who receives one HLA antibody-positive high risk component and two high risk components whose HLA status is unknown would have a probability of not developing TRALI equal to $(0.0159) \times (0.0018) \times (0.0018)$ and a probability of developing TRALI equal to $1-\{(0.01.59) \times (0.0018) \times (0.0018)\}$. Using this method, we estimated that the TRALI rates would be about 2.32% for case recipients and 0.79% for control recipients.

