The estimate of 0.79% for control recipients is close to the Finlay estimate (0.85%=7/820) as expected. The Finlay estimate is the TRALI incidence for recipients transfused with components of unknown HLA status. Knowing that one of the transfused components is HLA negative lowers the risk slightly, while the greater average number of components in the control group raises the risk slightly, for a net negligible change in the risk. The estimate of 2.32% in case recipients is less than the composite estimate for other lookback studies (2.7%=5/184). This too is expected, as the other lookback studies only considered components from donors who had been 'implicated' in a TRALI incident.

If the average number of transfused components per recipient were 4 rather than 6, then the TRALI rate estimates in the case recipient group and control recipients groups are lowered to 2.0% per case recipient and 0.5% per control recipient. The statistical power of the study increases as average number of components decreases. Conversely, the statistical power of the study decreases as the average number of components increases. If the interim analysis finds the average to be larger than 6, then increasing the sample size will be considered (see Appendix H). A one-sided 0.05 level test with samples of 1,175 in each of the two recipient groups will have 90% power to statistically detect a greater TRALI incidence among case recipients if 6 components are transfused (statistical power computed using StatXact for an exact conditional test comparing two binomial proportions).

Appendix E: Expected participating hospitals for LAPS-II: IRB, type of medical records, and difficulty in accessing records

No.	No. Participating Hospital Name		Type of IRB (check one)			Patient records (Check one)		On a scale of 1-5 how easy is it to obtain access to medical records?				
							Very easy			Very difficult		
		Hosp	Univ	Other	Electro- nic	Paper	1	2	3	4	5	
		Но	xwort	h Bloo	d Center			1				
1	University Hospital		X		Х		X					
2	Christ Hospital	Х			Х			Х				
3	Jewish Hospital	X			Х			х				
4	Good Samaritan	X			Х			х				
	Hospital											
	The	e Institu	ite for	Transf	fusion Me	edicine						
5	UPMC Presbyterian		Х		Х			Х				
6	UPMC Shadyside		Х		Х			х				
7	Children's Hospital of Pittsburgh of UPMC		X			Х			Х			
8	UPMC Passavant		х			х			Х			
9	UPMC St. Margaret		х		х				Х			
10	Magee-Women's Hospital of UPMC		X		Х				Х			
11	UPMC McKeesport		Х			Х			Х			

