Appendix H: Interim Analysis

The statistical power for the study is based on several assumptions, including the estimated incidence of TRALI/Possible TRALI. Other assumptions include the number of units transfused per transfusion episode. Although these assumptions are based on validated processes, such as, the published literature and the pilot data generated during the design of LAPSII, there remains a small possibility that the actual data may not show the expected incidence of TRALI in the two groups under study. Therefore, an internal pilot study will be performed to re-assess sample size (Tim Friede and Meinhard Kieser. 2004. Sample size recalculation for binary data in internal pilot study designs, Pharmaceutical Statistics, vol 3 p269-279).

The internal pilot study will result in an interim analysis. The interim analysis will be performed when the recipient record review process has been completed (including the review by the Medical Board) for 33% of subjects. At this juncture, the incidence of TRALI (including possible TRALI) will be calculated without un-blinding cases and controls. The internal pilot study data will allow improved estimates of TRALI incidence, and component distribution per transfusion episode to be computed. The sample size calculation as described in section H.4.will be re-done.

If the interim analysis suggests that an increase in the number of study recipients is needed, then two potential approaches are available. First approach will explore the possibility of completing the study with the larger sample size. The second approach will explore the possibility of reducing the power of the study, e.g., from 90% to 85% to reduce the degree of increase in sample size so that the increase in the number is not overwhelming. The use of internal pilot study data to re-assess sample size may have a modest effect on statistical power (A.L. Gould and W.J. Shih. 1998. Modifying the design of ongoing trials without unblinding, Statistics in Medicine, vol 17, p89-100). Therefore, reducing power to a nominal 85% may result in the effective power being on the order of 80%. In any event, changing the sample size will not affect type I error (i.e. 0.05 level test for analysis), as the sample size re-assessment will maintain blinding.

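### Components per episode, needed for the interim re-sizing and the per-unit incidences, would be counted only in the roughly 12% of recipients selected for x-ray, infiltrates and hypoxemia

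*Protocol*

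**What the plan says.** Appendix D builds the expected TRALI rates from the number of components a recipient receives: "Assume the number of components a recipient receives can be anything from 1 to 11, and averages 6". It says that power falls as that average rises.

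Section H4 makes the average one of two interim quantities: "The interim analysis will assess the average number of components per transfusion episode (assumed to be 6"). The other is TRALI incidence per component of unknown HLA status, assumed to be 0.18%. More subjects are considered if the average is much above 6 or the incidence much below 0.18%. Appendix H places this blinded look at 33% of subjects and states: "The internal pilot study data will allow improved estimates of TRALI incidence, and component distribution per transfusion episode to be computed".

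Section L plans per-component TRALI probabilities and incidence per unit transfused. On the source of the counts it says: "the number of units transfused per episode per patient will be derived from the data available in the data collection forms".

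On collection, F16 asks the blood bank about the study component only: patient, unit number, "the date and time the product was issued, type of component and whether there was any adverse event reported within 24 hours" of issue. F4 sets the condition for the detailed review in which the full extended form is completed: "If hypoxemia is documented, a detailed medical record review will be performed by the record review coordinator".

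**The concern.** The plan needs a component count that describes all study recipients, but its forms capture one only for recipients well along the pathway to a TRALI diagnosis. These patients are sicker by construction and plausibly receive more blood than the rest.

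Two outputs depend on the count. The first is the interim re-sizing. An inflated mean makes the average look too high. It also inflates the unit denominator, so incidence per component looks too low. One artifact could therefore move both H4 criteria toward a larger study. The second is the set of per-component and per-unit incidences in Section L, whose numerators would cover all recipients while their denominators rested on the subset.

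A statistical analysis plan cannot repair this, because the field is never collected. F19 keeps patient names and record numbers out of the central database, and F18 has the identity link destroyed at the end of the study.

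**Working it through.** **1. Where a count could be recorded**

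| Source | Who reaches it | What it holds on other components |
|---|---|---|
| F16 blood bank form; Screening Form Section A (Appendix F) | all 2,590 | nothing; study unit only |
| Screening Form Sections B and C | Section B ends without a post-transfusion x-ray; Section C ends if no extended review is required | nothing |
| Extended Form Section D (Appendix G) | about 518 (20%), before the hypoxemia stop | units in the 6 hours before onset of a reaction |
| Extended Form Section K | about 311 (12%), after the hypoxemia stop in Section E | unit counts for 24 hours before and 24 hours after the study unit |

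Section H6 adds identification of other units within 6 hours of onset, but only for TRALI cases. No other source or sampling scheme is described.

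**2. Coverage**

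Table 4: 2,590 × 0.40 = 1,036 with an x-ray; × 0.50 = 518 with infiltrates; × 0.60 = 311 with hypoxemia. 311/2,590 = 12.0%. The F6 pilot agrees: (2 + 6)/(22 + 44) = 8/66 = 12.1%. At the interim, 0.33 × 2,590 ≈ 855 recipients, of whom 855 × 0.12 ≈ 103 would have a Section K count.

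**3. Unit of measurement**

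Section H3 defines separate episodes by a gap of six hours between components. Section K uses fixed windows on either side of the study unit, so it can merge episodes. Even within the 12%, episode size is not recorded directly.

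**4. The plan's own sample size**

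Inputs from Appendix D: "A one-sided 0.05 level test with samples of 1,175 in each of the two recipient groups will have 90% power", and "we estimated that the TRALI rates would be about 2.32% for case recipients and 0.79% for control recipients". Enumerating the one-sided Fisher test over two binomials gives power of 90.0% at 1,175 per arm, 85.0% at 1,007 and 80.0% at 886. This matches the 9.0% prevalence row of Table 12.

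The rates also come back. Let S be the probability that the other components cause no TRALI:

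- S = 0.30 + 0.70 × Σ w(k) × (1 − 0.0018)^(k−1)
- case rate = 1 − (1 − 0.0159) × S
- control rate = 1 − (1 − 0.0004) × S

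Here 30% of study units are apheresis platelets with no other component (H3), and w(k) is the size-biased distribution of components per plasma episode. I assumed a triangular shape on 1 to 11 before size-biasing, because the protocol gives only range and mean. At mean 6, S = 0.9925 and the rates are 2.33% and 0.79%. At mean 4 they are 2.04% and 0.50%, against the stated 2.0% and 0.5%.

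**5. Sensitivity of n to the mean (illustration, same model and test)**

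| Mean components | Case / control rate | n per arm for 90% power | Power at 1,175 |
|---|---|---|---|
| 4 | 2.04% / 0.50% | about 933 | 95.5% |
| 6 | 2.33% / 0.79% | about 1,167 | 90.3% |
| 8 | 2.61% / 1.08% | about 1,397 | 84.5% |
| 10 | 2.90% / 1.37% | about 1,605 | 79.0% |

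The row at 6 differs slightly from 1,175 because the rates are unrounded.

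**6. What selection could do (assumed means, not from the documents)**

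If the 12% averaged 10 and the other 88% averaged 4, the true mean would be 0.12 × 10 + 0.88 × 4 = 4.7, needing roughly 1,000 to 1,050 per arm. The forms would show 10, which implies about 1,605.

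**The case against.** Several points on the other side stand.

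*The size of the bias is unknown.* A reader might infer from Table 11 (10.4 components at the university center against 2.6 and 3.1 at two community hospitals) that selection alone would make the forms read 8 or 10, and so raise the sample by 1,397/1,167 = 1.20 to 1,605/1,167 = 1.38 times. The documents do not support this.

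- Table 11 also has community hospitals at 5.9 and 10.8. The four community hospitals pooled give 6,562/1,052 = 6.2.
- Its figures are per admission and count single whole-blood platelet units. With H3's conversions (5 platelet units to one; 2.3 and 1.6 episodes), the university center gives (3,066 + 1,786 + 2,196/5)/676/2.3 = 3.4 per episode. The small community hospital gives (246 + 50 + 32/5)/107/1.6 = 1.8.
- The pilot's 6/44 against 2/22 going to extended review rests on eight events (Fisher p = 0.71). It moves the tertiary share only from 44/66 = 67% to 6/8 = 75%. With 3.4 and 1.8 per episode, the mean moves from (44 × 3.4 + 22 × 1.8)/66 = 2.9 to 0.75 × 3.4 + 0.25 × 1.8 = 3.0.

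Hospital mix therefore explains little. Sicker patients within a hospital may receive more units, but no figure in the protocol says how many more. H3 expects 3 to 4 per episode and takes 6 as conservative, so an inflated reading could still fall at or below 6 and change nothing.

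*Not every secondary estimate needs a count for everyone.* Three of the four quantities listed in Section L are per-component probabilities; the fourth is a proportion of TRALI. A representative sample of counts would serve. The contrast between positive and negative components is largely identified by the arm difference: 2.32 − 0.79 = 1.53 points, against 1.59 − 0.04 = 1.55.

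*The consequences are bounded.* The re-sizing is blinded and only considered, a much larger increase needs wider deliberation, and an overstated count errs toward more power.

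None of this supplies the missing counts or makes the 12% representative.

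**Conclusion.** The defect holds as a data-capture gap. As drafted, the interim mean and the unit denominators would rest on about 311 of 2,590 recipients (about 103 of 855 at the interim), selected on the path to the outcome and measured in windows that do not match the protocol's episode. On the broadest reading of Section D, coverage is still only about 20%, in a subset selected on x-ray and infiltrates.

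The bias is probably upward. It would then understate incidence per component and push both H4 criteria toward a larger sample. Its direction rests on the judgment that sicker recipients get more blood and that 24-hour windows merge episodes. Its size is not known, and the sample sizes at means of 4, 8 and 10 show only how sensitive the plan is.

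A reader might also infer that the main result is compromised. It is not: the primary analysis compares recipients, not units, and the blinded re-sizing leaves its type I error as planned. What is at risk is a misdirected interim decision, with its cost, and unreliable per-unit results. This should be fixed, before data collection or while the records can still be linked.

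**What to change.** Add a field to the Screening Form for every study unit: the number and type of all components given to that recipient in the same six-hour-gap episode. If that is too much work, collect it for a random sample stratified by center and hospital type. Use transfusion times where available and note which time was used, because Note 1 of Appendix F warns that issue and transfusion times can differ for operating and recovery rooms. State in H4, Appendix H and Section L that this field, not Section K, supplies the interim average and the per-unit denominators.

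The cost is one form revision and a few extra minutes per unit in a blood bank lookup that already takes place (Section N budgets ten minutes for each of 518 products per center). At an assumed 3 minutes, 518 × 3/60 ≈ 26 hours per center; a random sample would need proportionally less.

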The total number of components that would require review is 1,295 antibody positive plasma rich components and 1,295 antibody negative plasma rich components. These components will include all types of transfusable plasma (FFP, Plasma frozen within 24 hours of phlebotomy, cryoprecipitate-reduced plasma, concurrent plasma, thawed plasma and other transfusable plasma), apheresis platelets (plateletpheresis), and whole blood. Further, we estimate that 50% of components identified by the blood centers will be distributed to those hospitals where the record review will be performed. This is a conservative estimate and the percentage may in fact be higher. Based on this 50% rate, the number of plasma rich components that the project needs to identify totals 2,590 (1,295 x 2.0) from antibody positive donors and 2,590 (1,295 x 2.0) from antibody negative donors.

F8. Estimate of number of donations and components from LAPS donors: A preliminary analysis at the five participating REDS-II Centers has been performed to determine the number of HLA antibody positive plasma rich components that will be available for recipient record review. This analysis included the components from the index LAPS-I donations, all subsequent donations after the index LAPS donation, and all components distributed within 2 years prior to the index LAPS donation. Data collected from 75 LAPS-I donors have shown that during this

defined time interval, there were 694 plateletpheresis and 705 plasma components distributed from donations made by these donors. Therefore, we estimate that a total of 1,399 blood components (Plasma + Plateletpheresis) were available from 75 donors in this preliminary study; this averages to 18.5 components per donor. In order to obtain 2,590, antibody positive plasma rich components, we estimate that we will need to trace records from 140 antibody positive donors (28 per participating center). Similarly, we estimate the need for 140 antibody negative donors.

LAPS-I has identified 879 donors with HLA antibody at the five participating REDS sites, with a range of 108 to 219 HLA antibody positive donors per site. Thus the number of antibody positive LAPS donors at each one of the REDS-II site is sufficient to conduct the study.

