For blood donors from the LAPS, some donors without leukocyte antibodies will be excluded due to the fact that the number of antibody negative LAPS donors exceeds the numbers needed for this study.

K. Informed consent

Consent will be waived for blood donors since recipient investigation on blood donations from routine blood donors is a known part of general transfusion medicine practice. Also, there is no risk to the donors except for potential for loss of confidentiality of private health information. Safeguards will be in place to protect the confidentiality of the information. There will be a small risk that a donor who is not part of LAPS may be deferred from donating blood in the future if the donor is clearly implicated in a case of TRALI or is found to have antibodies upon recall testing. However, this risk is no different than if such a donor was found to be implicated or involved in a TRALI case that occurred outside of this study.

Informed consent from transfusion recipients is also waived because all recipient data will be obtained and maintained in a confidential manner and therefore the risk to the recipients is minimal from the loss of confidential private health information. The Centralized data will be maintained at Westat, the coordinating center for REDS-II research program. Westat has considerable experience in managing centralized database to ensure confidentiality of the donor and recipient data. All resulting publications will not contain recipient names or other personal identification information. The data will be linked to permit investigation of additional donors in those TRALI cases which are identified through the research and which were not previously reported to the blood bank. Potential for loss of confidentiality of private health information exists, but several safeguards will be in place to protect the information.

L. Data analysis

The primary analysis will compare the TRALI incidence among case recipients to the TRALI incidence among control recipients. Fisher's exact test for 2x2 tables will be used. The presumed statistical significance will imply HLA antibody in a transfused blood component is a risk factor for TRALI. Then secondary analysis will estimate;

- the probability of a HLA antibody-positive high risk component causing TRALI
- the probability of a HLA antibody-negative component causing TRALI
- the probability of a component of unknown HLA antibody status causing TRALI

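### The primary Fisher test and its 90% power treat recipients who share a donor as independent, so the stated power holds only if donor clustering is nil

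*Protocol*

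**What the plan says.** The arm is set by the donor. For each antibody-positive donor, Appendix D states that "we consider all of this donor's components in the study period, and enroll recipients of these components as case subjects"; it applies the same rule to antibody-negative donors and control subjects.

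F8 estimates that the study "will need to trace records from 140 antibody positive donors (28 per participating center"), at 18.5 plasma-rich components per donor, with the same number of negative donors. About half of the components are expected at participating hospitals. F8 also reports that "LAPS-I has identified 879 donors with HLA antibody at the five participating REDS sites", and H6 makes all of them eligible.

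H4 says "the sample size selected was 1,175 for the antibody positive components and 1,175 for the antibody negative components". Appendix D says "A one-sided 0.05 level test with samples of 1,175 in each of the two recipient groups will have 90% power", on the basis that "the TRALI rates would be about 2.32% for case recipients and 0.79% for control recipients", with "statistical power computed using StatXact for an exact conditional test comparing two binomial proportions". Section L makes the same kind of test primary: "Fisher's exact test for 2x2 tables will be used".

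The nearest assumption on independence is in H3: one study component per patient. H3, H4, L, Appendix D and Appendix H say nothing about recipients who share a donor.

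**The concern.** Recipients of the same donor's plasma share that donor's antibody class, strength, specificity and neutrophil-antibody status. C2 lists these as traits that may change TRALI risk, so the protocol itself expects risk to differ between donors. B5 suggests that one donor's neutrophil antibody may explain an unusually high reaction rate. H6 says most study donors have not been tested for neutrophil antibodies, so such donors could be in either arm.

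If risk varies by donor, events cluster. The 2,350 recipients then carry less information than 2,350 independent ones. At stake are the 90% power that justifies the sample size and, if clustering is strong enough, the 5% level of the test. Both are fixed in the protocol, so this is not a detail left to an analysis plan.

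**Working it through.** **1. The plan's own figure.** Inputs (Appendix D): 1,175 per arm, 2.32% against 0.79%, one-sided 0.05. Power is the sum, over all pairs of event counts, of the two binomial probabilities wherever the one-sided Fisher p-value is at most 0.05. Result: **0.900**. At 886 per arm it is 0.800, which matches Table 12. The stated power is therefore correct under independence. The test's true size is 3.1% with both arms at 0.79%, and 3.5% with both at about 1.56%, the mean of the two rates.

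**2. Recipients per donor.** 2,590 / 18.5 = 140 donors. 1,295 / 140 = 9.25 traceable components each; 1,175 / 140 = 8.4 after the 10% margin.

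**3. Effect of shared donors.** ICC and cluster-size spread are assumptions, because the protocol gives neither. Each donor's recipients follow a beta-binomial, with 140 donors and 1,175 recipients per arm and the same Fisher rule. Design effect DE = 1 + (m_A − 1) × ICC, where m_A = Σm²/Σm. For near-equal clusters m_A = 8.42; for unequal clusters (coefficient of variation about 1.1) m_A = 18.1. Example at ICC 0.05: 1 + 7.42 × 0.05 = 1.37 and 1 + 17.1 × 0.05 = 1.86. Type I error is shown for null rates of 0.79% to 1.56%.

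| ICC | Clusters | DE | Type I error | Power, planned test | n per arm for same information (1,175 × DE) |
|---|---|---|---|---|---|
| 0.01 | equal | 1.07 | 3.6–4.1% | 89.2% | 1,263 |
| 0.01 | unequal | 1.17 | 4.2–4.7% | 88.3% | 1,377 |
| 0.05 | equal | 1.37 | 5.5–6.1% | 86.5% | 1,611 |
| 0.05 | unequal | 1.86 | 8.1–9.0% | 83.2% | 2,181 |
| 0.10 | equal | 1.74 | 7.8–8.5% | 83.7% | 2,047 |
| 0.10 | unequal | 2.71 | 11.7–13.0% | 79.4% | 3,187 |

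Type I error passes 5% at an ICC of about 0.03–0.04 with equal clusters, or 0.0125–0.0175 with unequal ones.

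Where its size exceeds 5%, the planned test's power is flattered. A rough figure for a test that allows for clustering is Fisher power at 1,175/DE: 88% at DE 1.07, 85% at 1.17, 79% at 1.37 and 65% at 1.86.

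**4. Appendix D's risk structure.** There the index unit contributes only 0.04% of the 0.79% control risk. The other 0.75% comes from components of unknown status, given by other donors. If antibody status has no effect, the index unit contributes 0.18%, for a total of 0.18 + 0.75 = 0.93%. Suppose a share s of donors carries all index risk at rate r, so s = 0.18%/r. Then ICC = s(1 − s)r² / [π(1 − π)] with π = 0.93%. The values of r are assumptions, tied to figures in B5 and Table 3.

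- r = 2.9% (the B5 average): ICC 0.005, type I error 3.5–3.8%, power about 89%.
- r = 15% (3/20, the highest row without the outlier): s = 1.2%, ICC = 0.012 × 0.988 × 0.0225 / 0.00921 = 0.029, type I error about 5–6%, power about 82–86%.
- r = 42% (the outlier's raw rate): type I error about 7–9%, power roughly 73–80%.

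**The case against.** The strongest reply is that no error has been shown. The 90% follows exactly from its inputs, and any departure depends on an ICC that the documents do not supply. That stands: this is an unstated assumption, not faulty arithmetic.

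Second, a reader might infer that the 5% level is broken. The documents do not support that as a flat statement. Fisher's true size of about 3% absorbs small ICCs, and Appendix D places most background risk outside the index donor. Step 4 stays near or below 5% unless a few donors carry very high risk.

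Third, a reader might take an ICC from Table 3; a one-way analysis of variance without the outlier gives about 0.10. That is not a sound source. Its rows are studies of donors already implicated in TRALI, and they can differ in setting and review as well as donor. Only five events remain, and without the 3/20 row the estimate drops to 0.013. The outlier includes reactions too mild to be called TRALI.

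Fourth, 140 donors is a planning estimate, not a cap. F24B and H1 leave a selection procedure to be written, so a wider spread remains open. That too stands, but nothing currently requires it: Appendix D takes all components of each selected donor and sets no limit per donor.

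A separate analysis plan might add a clustered sensitivity analysis. That would not change the primary test or the power claim fixed here.

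**Conclusion.** The point holds in conditional form. Exposure is assigned by donor, about 8 to 9 recipients share each donor under the planning estimate, and neither the primary test nor the power calculation allows for it. Any positive ICC lowers the power below 90%: by 1 to 2 points at 0.01, about 4 to 7 at 0.05 and about 6 to 11 at 0.10 for the test as planned. The loss is larger for a test that holds its level.

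Type I error above 5% is possible but not established. It needs an ICC above roughly 0.01–0.04, or, under Appendix D's model, a few donors with very high risk. The main harm is overstated power. These figures take Appendix D's rates as given and rest on the assumed ICCs, the assumed cluster-size spread and 140 donors per arm.

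**What to change.** 1. Make the primary test donor-clustered. One choice is a permutation test that permutes antibody status among donors within the center by gender/parity matching cells. Report donor-clustered confidence intervals.
2. Restate the 90% power in H4 and Appendix D over a stated range of ICC and cluster-size spread, and say that the current figure assumes independence.
3. When the selection procedure foreseen in F24B and H1 is written, keep 1,295 components per arm but spread them over as many of the 879 positive donors, and matched negatives, as practicable, with a limit per donor. Using all 879 would give 1,295 / 879 = 1.5 components each. A limit of three, for example, needs at least 1,295 / 3 ≈ 432 donors per arm and holds the design effect to at most 1 + 2 × ICC, that is 1.10 at 0.05 and 1.20 at 0.10. In simulation with 800 donors per arm and ICC 0.05–0.10, even the unadjusted Fisher test had type I error of 4–5% and power of 89%.

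The cost is more donor look-ups at the blood centers and a less favourable stated power: slightly so if donors are spread widely, more so if 140 per arm are kept and the ICC is not small. No extra recipient charts are needed if the components are spread. Donor selection should be settled before data collection, because it cannot be repaired afterwards.
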